7.3.2 Evaluation of the primary endpoint

The primary endpoint will be assessed on the ITTm population. This criterion will be described according to the usual descriptive statistics. A one-sided 95% confidence interval will be calculated using the exact method.

The decision rules to be applied on 48 patients evaluable in the analysis (ITTm population) are:

- If 32 or fewer patients are alive without progression, then the treatment is considered ineffective.
- If 33 or more patients are alive without progression, then the treatment is considered effective.

These may be adjusted based on the actual number of evaluable patients included.

7.4 Evaluation of secondary efficacy criteria

7.4.1 Best response according to RECIST v1.1 criteria (as determined by investigator)

Population:

7.4.1.1 Definition

The best response is described by the rates of complete, partial, stable, progression, or non-evaluable response over the course of treatment. Response is assessed by the investigator according to RECIST V1.1 criteria.

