Planned study period	
Expected start date of inclusion: April 2013
 
Expected completion date of inclusion: April 2016
 
Expected completion date: July 2018

I. OBJECTIVES OF THE TRIAL

I.1 Main objective

Evaluate the investigator-assessed 9-month progression-free survival rate (according to RECIST 1.1 criteria).

I.2 Secondary objectives

Tolerance to treatment

Response rate according to RECIST 1.1 criteria at 9 months

Response rate according to EASL criteria, assessed at 9 months, by centralized review

Hepatic progression-free survival according to RECIST 1.1

Overall survival

Progression-free survival

Secondary resection rate

Evolution of tumor marker levels

II. PATIENT SELECTION

II.1 Inclusion criteria

Inclusion in the study requires that all of the inclusion criteria listed below be met:

- Histologically proven colorectal adenocarcinoma
- Radiologically or histologically proven liver metastases
- At least one measurable liver lesion according to RECIST v1.1 criteria
- Age \geq 18 years
- WHO Index \leq 2
- Life expectancy \geq 3 months
- No extra-hepatic disease, except pulmonary nodules if number \leq 3 and size $<$ 10 mm each
- Hepatic invasion $<$ 60%.
- Primary tumor resected or in place
- No prior chemotherapy for metastases (except peri-operative chemotherapy, if the last cycle was given at least 12 months ago)
- Adjuvant chemotherapy after resection of the primary site allowed if the last cycle was administered at least 12 months ago
- Normal liver function: total bilirubin \leq 1.5N, AST \leq 5N, ALT \leq 5N and PAL \leq 5N.

- TP \geq 60%
- Adequate hematologic function: PNN \geq 1500/mm³ , platelets \geq 100,000/mm³ , Hb \geq 9g/dL
- Good renal function: creatinine clearance \geq 60 mL/min
- No cardiac dysfunction: no cardiovascular events in the past 6 months or no NYHA \geq 2.

II.2 Non-inclusion criteria

Inclusion in the study requires that none of the non-inclusion criteria listed below are present:

- Patient eligible for curative treatment (resection and/or radiofrequency ablation) as determined by the PCR (including the opinion of a liver surgeon)
- Pregnant or breastfeeding women or patients of either sex of childbearing age who are not using an adequate method of contraception (see section V. 4)
- Previous cancer, except for non-melanoma skin cancers and curatively treated cervical in situ cancers. Other curatively treated cancers are allowed provided they have not recurred for more than 5 years

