The primary endpoint will be the proportion of patients alive without progression (death will be considered as progression) at 9 months after the start of treatment according to RECIST V1.1 criteria, as assessed by the investigator.

Progression-free survival time will be defined as the time interval between the date of inclusion and the date of progression or death (regardless of cause). For patients alive without progression, the time interval between the date of inclusion and the date of last morphological evaluation will be taken.

XII.2.2 Secondary Criteria

The secondary endpoints will be:

- Tolerance to the treatment
- Response rate according to RECIST v1.1 criteria at 9 months (according to the investigator)
- Response rate according to EASL criteria (assessed by centralized review) at 9 months
- Hepatic progression-free survival according to RECIST v1.1 criteria at 9 months
- Overall survival
- Progression-free survival
- The rate of secondary resections
- Changes in tumor marker levels

Liver progression-free survival will be defined as the time interval between the date of inclusion and the date of liver progression as assessed by the investigator's RECIST V1.1 criteria or death (regardless of cause) or the date of the last morphological assessment for patients alive without progression.

Overall survival will be defined as the time interval between the date of inclusion and the date of death regardless of the cause of death or the date of last news for living patients.

Tolerance to treatment will be assessed by:

- duration of treatment, doses received, dose reductions and deferrals
- Toxicities collected at each monthly visit, and described according to NCI-CTC version 4.0 criteria; Grade 3, Grade 4 and Grade 5 toxicities will be reviewed
- the number and description of SAEs

Changes in tumor marker levels (CEA and CA 19-9) will be assessed throughout the study.

XII.3 Calculation of the number of subjects needed

A 1-step Fleming design will be used, with a one-sided α risk of 5% and a power (1- β) of 90%.

The assumptions are:

- H0: A proportion of patients living without progression of 55% during the first 9 months is uninteresting;
- H1: A proportion of patients living without progression of more than 55% during the first 9 months would show the interest of the treatment; a proportion of 75% is hoped for.

Total number: **48 evaluable patients**

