3.1.2 Secondary objectives

The secondary objectives of the study are to evaluate:

- Tolerance to the treatment
- Best response according to RECIST v1.1 criteria (as determined by the investigator)
- Best response according to EASL criteria (evaluated in centralized review)
- Progression-free survival according to RECIST v1.1 criteria
- Progression-free survival
- Overall survival
- The rate of secondary resections
- Changes in tumor marker levels
- The maximum depth of response
- Early response rate (1^{ère} assessment at 8 weeks)

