Overall survival, progression-free survival	X	X		X
Progression-free survival at 9 months	X	X		X
Response rate (RECIST) at 9 months	X	X		X
Response rate (EASL) at 9 months (centralized review)	X	X		X
Secondary resection rate	X	X		X
Evolution of tumor marker levels	X	X		X
Tolerance				
Administration of the treatment (duration, dose received ...)			X	
Toxicities			X	
Exploratory analysis	X	X		X

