7.4.2.1 Definition

The best response is described by the rates of complete response, partial response, stability, and progression over the course of treatment. Response is assessed at the centralized review according to EASL criteria.

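### The SAP defines only best response on treatment; the 9-month RECIST and EASL response rates set by the protocol, and still listed in the SAP's own table, are left undefined

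*SAP*

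**What the plan says.** **Protocol.** The secondary endpoints in XII.2.2 give both response rates a time point. For RECIST the entry is "Response rate according to RECIST v1.1 criteria at 9 months (according to the investigator"; for EASL it is "Response rate according to EASL criteria (assessed by centralized review) at 9 months". Section I.2 agrees on EASL ("Response rate according to EASL criteria, assessed at 9 months, by centralized review"), and the synopsis gives the same time point for both criteria. None of these places says whether the rate means response status at month 9 or response reached by month 9.

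**SAP objectives and definitions.** Section 3.1.2 lists "Best response according to RECIST v1.1 criteria (as determined by the investigator" and "Best response according to EASL criteria (evaluated in centralized review", with no time point. The definition in 7.4.1.1 is "The best response is described by the rates of complete, partial, stable, progression, or non-evaluable response over the course of treatment". The EASL definition in 7.4.2.1 is "The best response is described by the rates of complete response, partial response, stability, and progression over the course of treatment"; it omits the non-evaluable category that RECIST has. The Population line is blank in both 7.4.1 and 7.4.2.

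**SAP analysis table and contents list.** The table at the start of section 7 has a row "Response rate (RECIST) at 9 months" and a matching EASL row, each marked for the ITT, ITTm and per-protocol populations. The contents list titles 7.4.2 as a 9-month EASL rate, while the heading in the body calls it best response.

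**The concern.** Best response on treatment and response at a fixed time are different estimands. A patient who responds at the first scan and progresses at month 6 is a best responder but is not in response at month 9. If the programmer follows the SAP definitions, the only quantity available is best response. Two things can then go wrong: the protocol endpoint is never computed, or a best-response figure fills the table row labelled 9 months.

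The trial has a single arm, so readers will judge its response rate against outside figures. The rationale in Protocol XIII itself cites time-point rates, including response at 9 and 12 months in the phase I study of DEBIRI with FOLFOX. A best-response figure would not be like-for-like with that precedent.

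**Working it through.** **1. Is there a planned figure to reproduce?** None for response: no expected rate or precision is given. The only design calculation concerns the primary endpoint (Protocol XII.3, SAP 4.3), and it reproduces:

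- n = ((1.645·√(0.55·0.45) + 1.282·√(0.75·0.25)) / 0.20)² = 47.14, rounded up to 48.
- Cut-off: 48·0.55 + 1.645·√(48·0.55·0.45) = 32.07, so success needs 33 or more.

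No response rate enters either formula, so this point leaves them unchanged.

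**2. The texts side by side.**

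| Place | RECIST | EASL |
|---|---|---|
| Protocol synopsis, I.2, XII.2.2 | 9 months | 9 months |
| SAP 3.1.2 | best response | best response |
| SAP 7.4.1.1 / 7.4.2.1 | best response on treatment | best response on treatment |
| SAP section 7 table | 9 months | 9 months |
| SAP contents list, 7.4.2 | – | 9 months |

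Sections 7.4.1 to 7.4.9 contain no definition of a 9-month response rate. The ±1 month scan window and the late-scan rules in 7.3.1 are written for the primary endpoint only. SAP 4.5 allows adjustments after an amendment or an unforeseen phenomenon, but the SAP cites neither for this change.

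**3. Direction.** Let B be the patients with CR or PR at any evaluation on treatment, and R the patients in CR or PR at month 9. Suppose both use the same denominator and nobody first responds after stopping treatment. Then everyone in R is also in B, so rate(B) ≥ rate(R). The excess comes from patients who responded and were no longer in response by month 9, and from those who first responded on treatment after month 9. The second group is possible because FOLFOX has no fixed end date (Protocol V.1 and VII).

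**4. Size.** It cannot be derived from the documents. As an illustration only, assume best response of 50–80% on 48 patients, with 0–40% of responders no longer in response at month 9 (counts rounded):

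| Best response | Responders lost by month 9 | Rate at month 9 | Gap (points) |
|---|---|---|---|
| 24/48 = 50.0% | 0% | 24/48 = 50.0% | 0 |
| 34/48 = 70.8% | 10% | 31/48 = 64.6% | 3/48 = 6.2 |
| 29/48 = 60.4% | 25% | 22/48 = 45.8% | 7/48 = 14.6 |
| 38/48 = 79.2% | 40% | 23/48 = 47.9% | 15/48 = 31.2 |

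**5. Which scan is the 9-month scan?** Protocol VII puts the first imaging at D63–D70 and then every 2 months. Counted from the start of treatment, this gives scans near months 8 and 10 and none at month 9. A 9 ± 1 month window runs from month 8 to month 10, so two scans can fall inside it. Borrowing the window alone does not settle which one counts.

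**The case against.** **The SAP has not clearly replaced the endpoint.** A reader might infer a completed switch from 9-month response to best response. The documents do not establish that, because the section 7 table still plans the 9-month rates. The contents list is weaker evidence, since its numbering does not match the body and it may simply not have been refreshed. The table also omits depth of response and early shrinkage, so it too may lag behind the text. Either way the SAP contradicts itself, and it does not say which text governs.

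**Best response need not always be the higher figure.** A reader might infer that the change can only flatter the treatment. That needs all the conditions in step 3 of the working. If the protocol means response reached by month 9, an early responder who later progresses counts under both definitions and the difference could be small. A patient who stops treatment before month 9 and first responds afterwards could count at 9 months but not under best response on treatment. The denominators are also open while the Population lines are blank. This objection stands, and it makes the direction conditional.

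**A maximum gap of 45 or 25 points does not follow.** It is tempting to subtract the progression-free proportions of 55% (H0) and 75% (H1) from 100%. But those proportions are only ceilings on 9-month RECIST response. Patients with stable disease are progression-free without being responders, so the 9-month rate can lie well below the ceiling and the difference of two upper bounds is not a bound on the gap. The ceiling also rests on investigator-assessed RECIST progression and does not carry over to centrally read EASL response.

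**The stakes are limited.** The response rates are secondary and purely descriptive, and 3.1.2 states best response openly. This is correct and sets the weight of the point, but it does not remove the need to settle what is reported.

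**Conclusion.** The inconsistency holds for both RECIST and EASL. The protocol and the SAP's own analysis table call for response at 9 months, while the SAP's objectives and definitions give only best response on treatment. As written, the 9-month rate may be missing from the results or may be a best-response figure under the wrong label.

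Best response is at least as high as the 9-month rate if the latter means status at month 9, the denominators are the same, and no one first responds after stopping treatment. The gap of 0 to about 31 points rests wholly on the assumed rates in the working and is not an estimate for this trial. The primary endpoint, the 48 evaluable patients and the 33-of-48 rule are unaffected. The point should be corrected, but it does not threaten the trial's main conclusion. Confidence is high on the mismatch and low on its numerical effect.

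**What to change.** Before the database is frozen, amend the SAP as follows:

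- In 7.4.1 and 7.4.2, define the protocol endpoint as CR+PR at the 9-month evaluation, by the investigator for RECIST and by central review for EASL.
- State the window and, if two scans fall within 9 ± 1 months, which one counts.
- Count patients who have progressed, died or have no evaluable scan by then as non-responders. SAP 6.3 leaves missing data unreplaced unless a rule is specified, so this one must be written down.
- Say how patients whose metastases were resected before month 9 are classified.
- Fill in the blank Population lines. Protocol XII.4 makes the evaluable (modified ITT) population the default for efficacy.
- Use the same non-evaluable category for RECIST and EASL.
- Keep best response as an additional endpoint under its own label.
- Align 3.1.2, the contents list and the section 7 table with these definitions.

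The cost is SAP wording and one more table. The reported 9-month response rate may look less favourable than best response.

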7.4.1.2 Evaluation

Rates will be described using standard statistics.

7.4.2 Best response according to EASL criteria (according to centralized review)

Population:

7.4.2.1 Definition

The best response is described by the rates of complete response, partial response, stability, and progression over the course of treatment. Response is assessed at the centralized review according to EASL criteria.

7.4.2.2 Evaluation

Rates will be described using standard statistics.

7.4.3 Depth of response (DpR)

Population:

7.4.3.1 Definition

It is defined as the relative difference between the sum of the largest diameters of RECIST target lesions at NADIR in the absence of new lesions or progression of non-target lesions and the sum of the largest diameters of RECIST target lesions at inclusion. It will be given according to the investigator and according to the centralized review of the images.

7.4.3.2 Evaluation

It will be described using standard statistics.

7.4.4 Early response rate (ETS: early tumor shrinkage)

Population:

7.4.4.1 Definition

Early (8-week) tumor shrinkage rate is defined as the relative difference between the sum of the largest diameters of the RECIST target lesions at 8 weeks and this sum at inclusion. Tumor shrinkage will be observed when the relative

difference is > 20% and > 30% (2 thresholds). It will be given according to the investigator and according to the centralized review of the images.

7.4.4.2 Evaluation

Rates will be described using standard statistics.

7.4.5 Hepatic progression-free survival according to RECIST v1.1 criteria

Population:

7.4.5.1 Definition

It is defined as the time interval between the date of inclusion and the date of 1^{ère} hepatic (radiological) progression or the date of death (from any cause). Patients alive and without progression will be censored at the date of last news.

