- If the following grade 3 or 4 toxicities occur as a result of chemoembolization, no additional session will be performed (but FOLFOX will be continued).

- Arteritis
- Grade 3 or 4 hepatic impairment
- Local ischemic and septic manifestations (cholecystitis, hepatic infarction, hepatic abscess, digestive hemorrhage) of grade 3 or 4
- Grade 3 or 4 renal insufficiency
- **The interval between chemoembolization sessions may be extended to allow for recovery of liver function.**
- No dose adjustment of irinotecan is planned for chemoembolization sessions.
- In case of hematological toxicity, FOLFOX dose adjustment rules **will be applied and chemoembolization will be continued.**

In case of doubt, do not hesitate to ask for advice from the study's referring radiologist, [name], through the FFCD.

VII. PATIENT MONITORING DURING TREATMENT AND AFTER WITHDRAWAL OF TREATMENT

Monitoring during treatment:

- **Before each cycle of FOLFOX:**
 - Complete clinical examination including: weight, vital signs, WHO, pain assessment (VAS)
 - Biological check-up: CBC/platelets
 - Adverse event evaluations according to NCI CTC version 4.0
- **Before each chemoembolization session**
 - Complete clinical examination including: weight, vital signs, WHO, pain assessment (VAS)
 - Biological workup consisting of measurements of hematological, nephrological and hepatic parameters: CBC/platelets, blood ionogram, creatinine, albumin, transaminases (AST, ALT), alkaline phosphatases (ALP), total and conjugated bilirubin, PT
 - Adverse event evaluations according to NCI CTC version 4.0

CEA and CA 19-9 assays, as well as thoracoabdomino-pelvic CT and liver MRI will be performed at an initial evaluation between D63 and D70 and then every 2 months after the start of treatment.

For patients participating in the associated 'lipid' translational study, please remember to perform the fasting sample and then technician the sample.

After the chemoembolization treatment period:

All patients will receive chemotherapy with FOLFOX every 2 weeks according to the usual regimen until progression or unacceptable toxicity.

VIII. STOP PROCESSING THE STUDY

The processing of the study will be stopped in case of:

- Investigator's decision
- Major toxicity requiring discontinuation of treatment (despite protocol adaptations)
- Serious or unexpected event requiring discontinuation of protocol treatment
- Progression of the disease
- Patient refusal or withdrawal of consent

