In all cases of treatment discontinuation, the patient remains in the analysis for intention-to-treat and overall survival, and for 30 days after the last study treatment for toxicity.

There is no exclusion period for a subsequent therapeutic trial.

IX. CENTRALIZED READING OF CT SCANS AND MRI

Responses will be evaluated according to RECIST version 1.1 criteria (Appendix 3) and will be reviewed by a panel of independent radiologists according to RECIST version 1.1 criteria and EASL criteria (Appendix 4).

Don't forget to keep the CDs and the report of the CT and MRI evaluation in the patient's file; the FFCD CRA will make a copy of these imaging assessments to centralize them at the CRGA on the 'FFCD Images' platform using a secure transmission via the company ETIAM.

X. MANAGEMENT OF SERIOUS ADVERSE EVENTS (SIA)

Safety will be assessed by evaluating the general, clinical and biological status of patients at the time of scheduled visits and by collecting events occurring between visits. Toxicities will be assessed using the NCI-CTC Toxicity Scale version 4.0 (Appendix 5).

X.1 Definitions

Adverse Event (AE)

An adverse event is a harmful occurrence in a person who is a subject of biomedical research, whether or not the occurrence is related to the research or the product being investigated. All adverse events will be recorded in the observation book on the pages provided.

Serious Adverse Event (SAE)

A serious adverse event is any event that meets at least one of the following criteria:

- Resulting in death,
- Life-threatening,
- Leading to hospitalization or prolonged hospitalization,
- Causing permanent disability or severe temporary incapacity,
- Causing a birth defect, fetal malformation or abortion,
- Medically significant (examples: overdoses, second cancers, pregnancies and new developments may be considered medically significant)

Pregnancy is an exclusion criterion in this trial.

However, if a pregnancy is discovered after inclusion, the patient must be excluded from the trial. The sponsor should be informed immediately via the Serious Adverse Event Reporting Form (no severity criteria should be checked). The patient should be followed until the outcome of the pregnancy and this outcome, whatever it may be, should be reported to the sponsor.

Hospitalizations included in the protocol will not be considered an SAE.

Undesirable Effect

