6.2 Agreements concerning dates and durations

Time since inclusion will be defined as the time since the day of inclusion, with the day of inclusion considered day 1. Therefore, the durations will be calculated according to the following rule, for example for the duration between death and inclusion: day of death - day of inclusion **+ 1**.

The day before the day of inclusion (resp. the day before the day of treatment) will be considered as day -1 (day 0 does not exist).

The last date of news will be the date of the last examination performed or the last treatment or the last medical consultation/visit.

The following conversion rules will be used to convert the number of days into months or years: 1 month = 30.4375 days; 1 year = 365.25 days.

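### SAP 7.4.5.1 does not say how progression outside the liver before liver progression is handled in hepatic progression-free survival

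*SAP*

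**What the plan says.** **Event.** SAP 7.4.5.1 ends hepatic PFS at the first "hepatic (radiological) progression or the date of death (from any cause").

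**Censoring in the SAP.** The same section continues: "Patients alive and without progression will be censored at the date of last news". It does not say whether progression here means liver progression or progression at any site. SAP 7.4.6.1 uses the same sentence for overall PFS, where any site is meant. SAP 6.2 defines the date: "The last date of news will be the date of the last examination performed or the last treatment or the last medical consultation/visit". No liver image is needed.

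**Censoring in the protocol.** Section XII.2.2 ends hepatic PFS at liver progression as judged by the investigator, "or death (regardless of cause) or the date of the last morphological assessment for patients alive without progression". The date differs from the SAP, and the word hepatic is again missing from the censoring clause.

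**Treatment and imaging.** Protocol VIII stops study treatment for "Progression of the disease", at whatever site. Under the subheading on monitoring during treatment, protocol VII says that CT and liver MRI "will be performed at an initial evaluation between D63 and D70 and then every 2 months after the start of treatment". After treatment stops, protocol VIII says "the patient remains in the analysis for intention-to-treat and overall survival, and for 30 days after the last study treatment for toxicity". It does not mention liver imaging.

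**Other rules.** SAP 6.3 does not replace missing data outside specified cases. SAP 7.4.5.2 asks for Kaplan-Meier rates at unspecified time points. The protocol's list of secondary endpoints names 9 months for hepatic PFS.

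**The concern.** Hepatic PFS is the time-to-event endpoint closest to a treatment delivered into the liver. It differs from overall PFS only through patients whose disease first progresses elsewhere. Such patients are foreseeable: eligibility allows up to three small lung nodules and a primary tumour in place, and the intra-arterial component treats only the liver.

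These are the patients for whom the rule is silent. Two statisticians could read the censoring sentence differently and draw different curves from the same data. On the more natural reading, time in which nobody is required to image the liver, possibly on another line of treatment, is counted as liver control.

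**Working it through.** The plan gives no figure for hepatic PFS, so there is none to reproduce. The first step is to apply the text to a case. The second is to size the effect on stated assumptions.

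**Step 1: apply the rule.** Take a patient with new lung lesions and a controlled liver at month 6, who then stops study treatment.

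- *Liver progression documented later:* event at that date. Defined.
- *Death at month 20 with no liver progression recorded:* event at month 20. Defined, but with no stated liver assessment between months 6 and 20.
- *Alive at analysis with no liver progression recorded:* on the any-site reading the patient is neither an event nor without progression, so there is no date, and SAP 6.3 supplies none. On the hepatic reading the patient is censored at last news. Under the protocol's date, with the same reading, the patient is censored at the last morphological assessment.

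**Step 2: size.** The documents give neither the share of first progressions that are extrahepatic nor survival after progression. The assumptions are:

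- Any-site PFS S at 9 months is 55% or 75%, the plan's uninteresting and hoped-for rates. The hazard of first progression is λ = −ln(S)/9, that is −ln(0.55)/9 = 0.0664 or −ln(0.75)/9 = 0.0320 per month.
- A share q of 20% or 40% of first progressions is extrahepatic, so the hazards are qλ outside the liver and (1−q)λ in it.
- Median time from first progression to death is 12 or 18 months (exponential).
- Follow-up is uniform over 27 to 63 months. In the synopsis timetable, April 2016 to July 2018 is 27 months and April 2013 to July 2018 is 63.
- Scans are every 2 months, with none of the liver once extrahepatic progression has been seen.

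I simulated 400,000 patients per scenario. The comparison is hepatic PFS if liver scans continued against hepatic PFS carried to death or last news. These rows span the range; differences come from unrounded values.

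| 9-month PFS | q | Median to death | 9 months: scanned / carried | Shift | 18 months: scanned / carried | Shift |
|---|---|---|---|---|---|---|
| 55% | 20% | 12 mo | 63.6 / 64.5 | +0.8 | 35.2 / 37.6 | +2.4 |
| 55% | 40% | 18 mo | 70.1 / 71.6 | +1.5 | 43.2 / 48.3 | +5.1 |
| 75% | 20% | 12 mo | 80.5 / 80.7 | +0.2 | 60.6 / 61.5 | +0.8 |
| 75% | 40% | 18 mo | 84.3 / 84.7 | +0.4 | 66.7 / 68.3 | +1.6 |

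The shift is therefore about 0.2-1.5 points at 9 months and 1-5 points at 18 months.

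**Sensitivity.** A second set-up used q of 10-40%, a 12-month median to death, last news at 15-51 months and progression dated without waiting for a scan. It gave +0.3 to +2.2 points at 9 months, +0.6 to +4.6 at 18 months, and a median 0.4-1.7 months longer. On the literal reading, 2.4-11.3% of patients had no end date: 0.024 × 58 = 1.4 to 0.113 × 58 = 6.6, about 1 to 7 of 58.

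**What the protocol's date achieves.** In the main set-up I kept deaths as events and censored living patients at their last liver scan. The 18-month shifts in the four rows fell to +1.8, +3.0, +0.6 and +0.9 points. The curve is less favourable, but part of the shift remains because deaths still count at the date of death.

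**The case against.** **The natural reading.** The section is headed hepatic PFS and its event is hepatic progression, so progression in the next sentence most naturally means hepatic. On that reading every patient has an end date. This stands. A reader might infer that patients who progress outside the liver first have no valid end date at all. The text does not support that: only the living patient without liver progression lacks one, and only on the literal reading.

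**Deaths.** Death from any cause is a stated event, so a death at month 20 counting as 20 months is what this composite is built to do. That also stands. Whether time on a later line should count is a choice of estimand, not a contradiction.

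**Imaging.** The title of protocol VII covers the period after treatment withdrawal, and the two-monthly schedule has no stop date. A reader might infer that later liver progression is certain to go unseen. The documents do not establish that; they are silent. But they do not require continued liver imaging either, and censoring at last news does not depend on it.

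**Size.** The 9-month shift is small, and the top of the 18-month range arises only when 9-month PFS is 55%. With 58 patients and no censoring, a 95% interval near 50% has a half-width of about 1.96 × √(0.5 × 0.5/58) = 0.129, or 13 points. This limits the weight of the point but does not remove it: the shift is in one direction and wording can reduce it.

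**Conclusion.** The gap is real. Neither document says how extrahepatic progression before liver progression enters hepatic PFS, and the SAP and protocol disagree on the censoring date. Followed on its natural reading, the SAP counts these patients as free of liver progression to last news or death without requiring a liver image. That favours the treatment by roughly 0.2-1.5 points at 9 months and 1-5 points at 18 months. These figures rest on assumed extrahepatic shares, post-progression survival and no further liver scans, none of which the documents give.

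Hepatic PFS is a descriptive secondary endpoint with no test or decision rule. A reader might infer that the trial's efficacy decision is affected; it is not, because the primary endpoint counts progression at any site and has its own rules in SAP 7.3.1. Nor do the documents support replacing the protocol's composite with a competing-risk analysis as the lead result. The correction should be made, but it is one of definition and supportive reporting.

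**What to change.** 1. In SAP 7.4.5.1, say that patients alive and without *hepatic* progression are censored, and clarify protocol XII.2.2 in the same way.
2. Reconcile the censoring date with protocol XII.2.2: use the last morphological assessment, specified as the last one that imaged the liver, instead of last news.
3. Keep hepatic PFS as the protocol-listed secondary endpoint.
4. Report the number of patients whose first progression was extrahepatic.
5. Add, as a supportive analysis, the cumulative incidence of hepatic progression, with extrahepatic-first progression and death without hepatic progression as competing events, each dated at the assessment or death that showed it. It is needed because item 2 alone leaves part of the shift. It estimates a different quantity, so it belongs beside the composite curve, not in its place.

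The cost is a wording change and one standard analysis on data already collected, with no new scans. The hepatic PFS curve will be slightly less favourable and censored earlier. SAP 4.5 requires changes to be made before the database is frozen.
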